## 4.2. Scientific Rationale for Study Design

Achondroplasia is a disease of abnormal endochondral ossification at growth plates, therefore the ability to affect this process only exists whilst these growth plates are open. Fusion of growth plates varies across anatomical sites occurring very early in life for some cranial and spinal ossification centers, but persisting until adolescence in the long bones. Treatment with recifercept is only of potential benefit to those with open growth plates, thus this trial will only include children that are still growing in height.

Human reproductive safety data are not available for recifercept, but there is no suspicion of human teratogenicity based on the intended pharmacology of the compound. Therefore, the use of a highly effective method of contraception is required (see [Appendix 4](#)). Given the age of the participants in the study, abstinence is the only acceptable form of contraception.

Participants aged less than 3 years at enrollment will continue to undergo MRI scanning of the brain and cervical spinal cord every 12 months up to the age of 5 years. Complications at the craniocervical junction are amongst the most serious complications seen in achondroplasia and are particularly prevalent in those under 2 years. MRI scanning in very young children with achondroplasia is being widely adopted and standard of care.

Serum and **CCI** samples will be taken during the study as indicated in the [SoA](#). Further details can be found in [Section 8.6](#).

### 4.2.1. Participant Input into Design

Patient advocacy groups and patient experts assisted with review of the protocol, including attending the final medical advisory board meeting on Phase 2 design. The assessments conducted in this protocol are the same as the C4181005 Phase 2 study.

#### **4.2.2. Diversity of Study Population**

Reasonable attempts will be made to retain participants to ensure the study population is representative of the patient population that will use recifercept in clinical practice.

#### **4.2.3. Adjudication Committee**

Not Applicable.

#### **4.2.4. Choice of Contraception/Barrier Requirements**

Studies to evaluate the development toxicity of recifercept have not been conducted. Therefore, the use of a highly effective method of contraception is required (see [Appendix 4](#)).

#### **4.3. Justification for Dose**

All participants will continue to receive 1 of 3 doses of recifercept (1 mg/kg QW, 2 mg/kg BIW or 1.5 mg/kg QD) as assigned in C4181005 study or at the therapeutic dose once this is identified. Dose will be adjusted according to weight every 3 months.

PK will be assessed on an ongoing basis using sparse sampling approach to inform and update the PopPK model.

Weight limits for this study ([Section 5.2](#)) are based on technical feasibility of dosing with the current study intervention formulation such that injection volumes will be between 0.2 mL and 1 mL.

#### **4.4. End of Study Definition**

The end of the study is defined as the date of the last visit of the last participant in the study or last scheduled procedure shown in the [SoA](#) for the last participant in the trial globally.

A participant is considered to have completed the study if he/she has completed all periods of the study, including the last visit or the last scheduled procedure shown in the [SoA](#).

- The participant has reached end of puberty (Tanner Stage V);
- The participant is enrolled in any other interventional study;
- The participant is to receive any growth hormone, IGF-1, anabolic steroids, or any other drug expected to affect growth velocity.

### **5. STUDY POPULATION**

This study can fulfill its objectives only if appropriate participants are enrolled. The following eligibility criteria are designed to select participants for whom participation in the study is considered appropriate. All relevant medical and nonmedical conditions should be taken into consideration when deciding whether a particular participant is suitable for this protocol.

Prospective approval of protocol deviations to recruitment and enrollment criteria, also known as protocol waivers or exemptions, is not permitted.

### **5.1. Inclusion Criteria**

Participants are eligible to be included in the study only if all of the following criteria apply:

#### **Age and Sex:**

1. Male and female participants between the ages of  $\geq 15$  months to  $\leq 12$  years inclusive, at Visit 1 (Screen 1).
  - Refer to [Appendix 4](#) for reproductive criteria for male ([Section 10.4.1](#)) and female ([Section 10.4.2](#)) participants.

#### **Type of Participant and Disease Characteristics:**

2. Participants who are willing and able to comply with all scheduled visits, treatment plan, laboratory tests lifestyle considerations and other study procedures.
3. Completed the C4181005 Phase 2 study.
4. Able to stand independently for height measurements (if  $\geq 2$  years of age at enrollment).

#### **Informed Consent:**

5. Capable of giving signed informed consent/assent as described in [Appendix 1](#), which includes compliance with the requirements and restrictions listed in the ICD and in this protocol.
6. Following receipt of oral and written information about the trial, the child (depending on local IRB/independent EC requirements) must provide assent, and 1 or both (according to local regulations) parent(s) or legal guardians of the child must provide signed informed consent before any trial-related activity is carried out.

### **5.2. Exclusion Criteria**

Participants are excluded from the study if any of the following criteria apply:

#### **Medical Conditions:**

1. Presence of co-morbid conditions or circumstances that, in the opinion of the investigator, would affect interpretation of growth data or ability to complete the trial procedures.

2. Other medical or psychiatric condition including recent (within the past year) or active suicidal ideation/behavior or laboratory abnormality that may increase the risk of study participation or, in the investigator's judgment, make the participant inappropriate for the study.
3. Presence of severe obesity (BMI >95th percentile on Hoover-Fong BMI charts) [Hoover-Fong et al, 2008].
4. Known closure of long bone growth plates (cessation of height growth).
5. Body weight  $\geq$ 45 kg.
6. History of hypersensitivity to study intervention or any excipients.

**Prior/Concomitant Therapy:**

7. Current use of any prohibited concomitant medication(s) or those unwilling/unable to use a permitted concomitant medication(s). Refer to [Section 6.8](#) Concomitant Therapy.
8. History of any prior treatment with human growth hormone or related products (including IGF-1).
9. History of receipt of any treatment that are known to potentially affect growth (including oral steroids >5 days in the last 6 months, high dose inhaled corticosteroids (>800  $\mu$ g/day beclomethasone equivalent) and medication for attention deficit hyperactivity disorder).
10. History of limb lengthening surgery (defined as distraction osteogenesis/Ilizarov/callostasis technique following submetaphyseal osteotomy to extend bone length).
11. Any limb lengthening/corrective orthopaedic surgery planned at any point during the trial period.
12. Less than 6 months since fracture or surgical procedure of any bone determined from the screening visit date.
13. Presence of any internal guided growth plates/devices.
14. History of removal of internal guided growth plates/devices within less than 6 months.

**Prior/Concurrent Clinical Study Experience:**

15. History of receipt of any other (except recifercept) IP for achondroplasia or that may affect growth/interpretation of growth parameters.

16. Previous administration with an investigational drug (not for achondroplasia/growth affecting) within 30 days (or as determined by the local requirement) or 5 half-lives preceding the first dose of study intervention used in this study (whichever is longer).

**Other Exclusions:**

17. Investigator site staff or Pfizer employees directly involved in the conduct of the study, site staff otherwise supervised by the investigator, and their respective family members.

**5.3. Lifestyle Considerations**

**5.3.1. Contraception**

Participants that become a WOCBP (defined as reaching menarche) during the course of the study, the investigator or his or her designee, in consultation with the participant, will confirm that the participant has been informed of the potential risks of pregnancy whilst receiving study intervention and advised of the need for continuing total abstinence from sexual activity (see [Appendix 4 Section 10.4.4](#)). At time points indicated in the SoA, the investigator or designee will inform the participant of the need to use continue total abstinence from sexual activity and document the conversation and the participants affirmation in the participants' chart. This also applies to males should they become sexually active. In addition, the investigator or designee will instruct the participant to call immediately if total abstinence from sexual activity is discontinued or if pregnancy is known or suspected in the participant or partner.

**5.4. Screen Failures**

Screen failures are defined as participants who consent to participate in the clinical study but are not subsequently randomly assigned to study intervention. A minimal set of screen failure information is required to ensure transparent reporting of screen failure participants to meet the CONSORT publishing requirements and to respond to queries from regulatory authorities. Minimal information includes demography, screen failure details, eligibility criteria, and any SAE.

Individuals who do not meet the criteria for participation in this study (screen failure) may be rescreened.

**5.5. Criteria for Temporarily Delaying Enrollment/Randomization/Administration of Study Intervention**

Not Applicable.

**6. STUDY INTERVENTION(S) AND CONCOMITANT THERAPY**

Study intervention is defined as any investigational intervention(s), marketed product(s), placebo, medical device(s), or study procedure(s) intended to be administered to a study participant according to the study protocol.

For the purposes of this protocol, study intervention refers to recifercept (PF-07256472) provided as lyophilized powder for solution for injection/infusion, 50 mg/vial.

Further details for the sections below can be found in the IP Manual and/or dosing diary.

### 6.1. Study Intervention(s) Administered

Intervention Name	PF07256472 (Recifercept).
ARM Name (group of patients receiving a specific treatment (or no treatment))	Recifercept
Type	Biologic.
Dose Formulation	Lyophilized powder for solution for injection.
Unit Dose Strength(s)	50 mg/vial.
Dosage Level(s)	1mg/kg - QW 2mg/kg - BIW 1.5mg/kg - QD
Route of Administration	SC injection.
Use	Experimental.
IMP or NIMP	IMP.
Sourcing	Provided centrally by the sponsor.  Refer to the IP Manual for further information.
Packaging and Labeling	Study intervention will be provided in vials. Each vial will be labeled as required per country requirement. The IP will be provided as open label supplies. Vials are single-use only.
Current/Former Name(s) or Alias(es)	TA-46.

#### 6.1.1. Administration

Administer study intervention according to the SC Dosing Instructions (see [Appendix 8](#)). Study intervention should not be self-administered by the participant.

#### 6.1.2. Medical Devices

Not Applicable.

### 6.2. Preparation, Handling, Storage, and Accountability

1. The investigator or designee must confirm appropriate temperature conditions have been maintained during transit for all study interventions received and any discrepancies are reported and resolved before use of the study intervention.
2. Only participants enrolled in the study may receive study intervention and only authorized site staff may supply. All study interventions must be stored in a secure, environmentally controlled, and monitored (manual or automated recording) area in accordance with the labeled storage conditions with access limited to the investigator and authorized site staff. At a minimum, daily minimum and maximum temperatures for all site storage locations must be documented and available upon request. Data

- for nonworking days must indicate the minimum and maximum temperatures since previously documented for all site storage locations upon return to business.
3. Any excursions from the study intervention label storage conditions should be reported to Pfizer upon discovery along with any actions taken. The site should actively pursue options for returning the study intervention to the storage conditions described in the labeling, as soon as possible. Once an excursion is identified, the study intervention must be quarantined and not used until Pfizer provides permission to use the study intervention. Specific details regarding the definition of an excursion and information the site should report for each excursion will be provided to the site in the IP manual.
  4. Any storage conditions stated in the SRSD will be superseded by the storage conditions stated on the label.
  5. Study interventions should be stored in their original containers.
  6. Site staff will instruct participants on the proper storage requirements for take-home study intervention.
  7. See the IP manual for storage conditions of the study intervention once reconstituted and/or diluted.
  8. The investigator, institution, or the head of the medical institution (where applicable) is responsible for study intervention accountability, reconciliation, and record maintenance (ie, receipt, reconciliation, and final disposition records), such as the IPAL or sponsor-approved equivalent. All study interventions will be accounted for using a study intervention accountability form/record. All study intervention that is taken home by the participant, both used and unused, must be returned to the investigator by the participant. Returned study intervention must not be redispensed to the participants.
  9. Further guidance and information for the final disposition of unused study interventions are provided in the IP manual. All destruction must be adequately documented. If destruction is authorized to take place at the investigator site, the investigator must ensure that the materials are destroyed in compliance with applicable environmental regulations, institutional policy, and any special instructions provided by Pfizer.

Upon identification of a product complaint, notify the sponsor within 1 business day of discovery as described in the IP manual.

### **6.2.1. Preparation and Dispensing**

See the IP manual for instructions on how to prepare the study intervention for administration. Study intervention should be prepared and dispensed by an appropriately qualified and experienced member of the study staff (eg, physician, nurse, physician's assistant, nurse practitioner, pharmacy assistant/technician, or pharmacist) as allowed by local, state, and institutional guidance. A second staff member will verify the dispensing. All persons who are responsible for dose preparation and dispensing of IP must be listed on the Delegation of Authority log.

Recifercept may be shipped by an appropriate third-party courier to study participants if permitted by local regulations and in accordance with storage and transportation requirements for recifercept.

Caregivers will reference the Dosing Instructions Diary for instructions on how to prepare and administer the study intervention at home, following demonstration of their proficiency at the site.

Adequate caregiver competency for home-dosing may include, but not be limited to the following criterion:

- Caregivers demonstrate adequate adherence to storage and preparation routine including sterile technique.
- Caregivers understand which sites can be used for injection and the need to rotate these sites.
- Caregivers demonstrate correct techniques to reconstitute and draw up solution into syringe for administration.
- Caregivers demonstrate correct injection technique including preparation of skin prior to injection.
- Caregivers show knowledge of adequate disposal of used medication supplies and completion of dosing diary.

The caregiver should be instructed to maintain the study intervention in the vials and cartons provided, throughout the course of dosing, and return the vials, in the cartons provided, to the site at the next study visit.

### **6.3. Measures to Minimize Bias: Randomization and Blinding**

There is no blinding requirement in this open label study.

### **6.3.1. Allocation to Study Intervention**

This is an open-label study; however, the specific study intervention dispensed to the participant will be assigned using an IRT. The site will contact the IRT prior to the start of study intervention administration for each participant. The site will record the study intervention assignment on the applicable CRF, if required.

The investigator's knowledge of the treatment should not influence the decision to enroll a particular participant or affect the order in which participants are enrolled.

Study intervention will be dispensed at the study visits summarized in the [SoA](#).

Returned study intervention must not be redispensed to the participants.

The study-specific IRT reference manual and IP manual will provide the contact information and further details on the use of the IRT system.

### **6.3.2. Breaking the Blind**

Not applicable.

## **6.4. Study Intervention Compliance**

When participants are dosed at the site, they will receive study intervention directly from the investigator or designee, under medical supervision. The date and time of each dose administered in the clinic will be recorded in the source documents and recorded in the CRF. The dose of study intervention and study participant identification will be confirmed at the time of dosing by a member of the study site staff other than the person administering the study intervention.

The site will complete the required dosage Preparation Record located in the IP manual. The use of the Preparation Record is preferred, but it does not preclude the use of an existing appropriate clinical site documentation system. The existing clinical site's documentation system should capture all pertinent/required information on the preparation and administration of the dose. This may be used in place of the Preparation Record after approval from the sponsor and/or designee.

When participants are dosed at home, compliance will be monitored by completion of a dosing diary by the caregiver which will record date, time, injection site and volume of dose administration. This diary will be reviewed by the site staff. Where home nursing has supported home dosing then this will be recorded in the dosing diary. Deviation(s) from the prescribed dosage regimen should be recorded in the CRF.

A record of the number of vials dispensed to and taken by each participant must be maintained and reconciled with study intervention and compliance records. Intervention start and stop dates, including dates for intervention delays and/or dose reductions, will also be recorded in the CRF.

If poor compliance is identified by site staff, then additional training and support will be provided to the caregivers.

#### 6.4.1. Participant Compliance and Home Administration

Caregivers will be permitted to administer recifercept once they have demonstrated an understanding of the preparation and administration process at the site. Confirmation of a caregiver's ability to perform preparation and administration must be documented in the site file. For administration of recifercept at home, compliance and any injection site reactions will be captured and completed by the caregiver by completing the dosing diary. Caregivers should contact the site immediately in the event of any potential injection site reactions.

Caregivers will administer treatment from the point of which they have demonstrated the capability to do so (as stated above) until the end of dosing. Prior to administration at home, sites must ensure caregivers are trained on IP administration and storage per the dosing diary. Dosing between planned clinic visits may be administered by investigational site staff until the respective caregiver has been properly trained in administration. Sites should follow up (eg, via phone call) to ensure compliance with administration instructions, where necessary. Clinic administration of study intervention can be readministered at any time where home dosing is deemed not feasible or inappropriate. Caregivers will be supported to reinstitute home dosing where appropriate.

A home health care service may be utilized to facilitate certain activities per the [Schedule of Activities](#), or when additional caregivers are trained. Any requests for home health support should be submitted to the sponsor for approval.

#### 6.5. Dose Modification

This protocol allows some alteration from the currently outlined dosing schedule, but the maximum daily dose will not exceed 1.5 mg/kg QD.

In case a dose reduction is necessary, the study intervention will be administered as follows:

High Dose (1.5 mg/kg QD)	Participants experiencing continued tolerability issues such as injection site reactions may be reduced to 2 mg/kg BIW and then if required to 1 mg/kg QW.
Medium Dose (2 mg/kg BIW)	Participants experiencing continued tolerability issues such as injection site reactions may be reduced to 1 mg/kg QW, if persistent then participant should be discontinued.
Low (1 mg/kg QW)	Participants experiencing continued tolerability issues such as ISRs should be discontinued from the study.

Participants that have been switched to any lower dose must stay on that dose for the remainder of the study.

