### **8.3.8. Adverse Events of Special Interest**

Injection site reactions will be considered an AESI. Injection site reactions may include but are not limited to erythema, induration, ecchymosis, pain and pruritis. The size and severity of these symptoms or reactions will be assessed and documented. The following details will be collected:

- Date of onset and resolution of the ISR;
- Presence of the following features on a mild/moderate/severe grading scale:
  - Erythema;
  - Induration;
  - Pain;
  - Swelling;
  - Pruritis.
- Did the ISR lead to any missed or delayed doses?
- Did the ISR lead to withdrawal of the participant from the study?

AESIs are examined as part of routine safety data review procedures throughout the clinical trial and as part of signal detection processes.

All AESIs must be reported as an AE or SAE following the procedures described in [Sections 8.3.1](#) through [8.3.4](#). An AESI is to be recorded as an AE or SAE on the CRF. In addition, an AESI that is also an SAE must be reported using the CT SAE Report Form.

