### *Safety*

The safety data will be summarized in accordance with Pfizer Data Standards. All participants who receive IP (safety population) will be included in the safety analyses. All safety data will be summarized descriptively through appropriate data tabulations, descriptive statistics, categorical summaries, and graphical presentations. Safety endpoints for the study include:

- TEAEs and SAEs;
- Withdrawals from treatment due to AEs.

Change from baseline in laboratory data and vital signs will be additionally summarized. Participant listings will also be produced for these safety endpoints.

The primary efficacy estimand will be the population treatment effect of the mean change-from-baseline of a continuous response (ie, height, growth) at month 24 irrespective of IP compliance. Increase in height growth above expected growth in reference population, a co-primary endpoint, is defined as the height growth in the achondroplasia reference population +50%. Intercurrent event for the efficacy estimand: withdrawal and all events leading missing data will be excluded from efficacy analysis and will not have their data imputed. The population-based treatment effect will be the mean change-from-baseline at Month 24.

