3. ANALYSIS SETS (POPULATIONS FOR ANALYSIS)

Data for all participants will be assessed to determine if participants meet the criteria for inclusion in each analysis population prior to unblinding and releasing the database and classifications will be documented per standard operating procedures.

Population	Description
Full Analysis Set (FAS)/Safety	All participants receiving at least one dose of recifercept. Participants will be analyzed according to the dose they actually received.
Randomized (RAS)	All participants receiving at least one dose of recifercept. Participants will be analyzed according to the dose assigned from C4181005.
Per-Protocol Analysis Set (PPAS)	All participants receiving at least one dose of recifercept and have complete data at baseline through end of study or subject discontinuation and without protocol deviations that were thought to impact the efficacy evaluation during the treatment period. Participants will be analyzed according to the randomized intervention. Participants will be analyzed according to the dose assigned from C4181005.
PK Concentration set	All participants who received at least one dose of recifercept and have at least one evaluable concentration.

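### AE-withdrawal rates are not comparable across doses, because Protocol 6.5 offers step-downs only from the two higher doses and no summary of AE-related dose reductions is named

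*Protocol*

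**What the plan says.** **The ladder (Protocol 6.5).** The trigger, continued tolerability problems, is the same in all three rows. The consequence differs.

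- 1.5 mg/kg QD: participants "may be reduced to 2 mg/kg BIW and then if required to 1 mg/kg QW". The row names no step after that.
- 2 mg/kg BIW: participants "may be reduced to 1 mg/kg QW, if persistent then participant should be discontinued".
- 1 mg/kg QW: "Participants experiencing continued tolerability issues such as ISRs should be discontinued from the study".

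A step-down is permanent: "Participants that have been switched to any lower dose must stay on that dose for the remainder of the study".

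**What is summarised.** Tolerability of the doses and regimens is part of a primary objective, and tables are presented by dose (Protocol 3 and 9.3.1). The safety endpoints in Protocol 9.3.2 are TEAEs and SAEs, and "Withdrawals from treatment due to AEs". SAP 5.6 also names withdrawal due to AEs. Neither list includes dose reduction due to AEs. The exposure summary in SAP 5.5.3 covers applications, dosing days and compliance.

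**What is collected.** Protocol 6.4 has intervention start and stop dates recorded, "including dates for intervention delays and/or dose reductions, will also be recorded in the CRF". The ISR follow-up items in Protocol 8.3.8 include "Did the ISR lead to any missed or delayed doses" and an item on withdrawal from the study. None asks about reduction.

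**How participants are grouped.** For the FAS/Safety set, SAP 3 says: "Participants will be analyzed according to the dose they actually received". It does not say where a child who received two or three doses belongs. SAP 3 also defines a Randomized set (RAS) by the dose assigned from C4181005, but no stated safety analysis uses it.

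**The concern.** A child who cannot tolerate daily dosing but continues on a lower dose contributes no withdrawal. A child with the same continued intolerance on the weekly dose contributes one. The by-dose withdrawal row thus mixes how well a regimen is tolerated with how many steps lie below it. The consequence that would restore the comparison, the reduction itself, is in the database but in no named table.

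Grouping by dose received can add to this. A child who starts on QD, steps down twice and then stops is on 1 mg/kg QW at the time of stopping, and could be counted against that dose.

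The study continues three regimens until a therapeutic dose is identified, and a committee monitors safety throughout. Someone reading the withdrawal row across doses could draw the wrong conclusion about which regimen children can stay on.

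**Working it through.** The plan gives no figure to reproduce: there are no hypotheses (SAP 4.1) and no assumed event rates. What follows is an illustration of direction and possible size.

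**Inputs**

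- Step-downs available: QD 2, BIW 1, QW 0 (Protocol 6.5).
- Children per dose: 21, assumed as 63/3. The documents give about 63 in total and no split.
- *q*, the probability of continued intolerance at the assigned dose: assumed equal in all three groups.
- *r*, the probability that it persists after each step-down: assumed the same at each step.
- All permitted step-downs are used, and a QD child who reaches 1 mg/kg QW then follows the QW row. The second part is an assumption, because the QD row names no end step.

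**Withdrawal probability by assigned dose**

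- QW: *q*
- BIW: *q* × *r*
- QD: *q* × *r*²

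**Expected withdrawals of 21, with equal true intolerance**

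| *q* | *r* | QW | BIW | QD |
|---|---|---|---|---|
| 0.2 | 0.2 | 4.2 | 0.84 | 0.17 |
| 0.2 | 0.5 | 4.2 | 2.1 | 1.05 |
| 0.2 | 0.8 | 4.2 | 3.4 | 2.7 |
| 0.2 | 1.0 | 4.2 | 4.2 | 4.2 |
| 0.1 | 0.5 | 2.1 | 1.05 | 0.53 |

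Worked for the second row: 21 × 0.2 = 4.2; 21 × 0.2 × 0.5 = 2.1; 21 × 0.2 × 0.5² = 1.05.

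For any *r* below 1 the count falls as the starting dose rises. An *r* below 1 is plausible, since the ladder takes planned injections per week from 7 to 2 to 1 and the weekly amount from 10.5 to 4 to 1 mg/kg.

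**When would the counts match?** QD intolerance must be 1/*r*² times QW intolerance: 4 times at *r* = 0.5 (0.40 against 0.10) and about 1.6 times at *r* = 0.8 (1/0.64).

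**Effect of grouping by dose received.** Take *q* = 0.2, *r* = 0.5 and attribute each withdrawal to the dose in use at the time. Under this model every withdrawal happens on 1 mg/kg QW, so the counts become 4.2 + 2.1 + 1.05 = 7.35 for QW and 0 for the other two. The same children give 4.2/2.1/1.05 or 7.35/0/0, depending on a rule the SAP does not state.

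**With the composite.** If the event is the first AE-related reduction or discontinuation, by assigned dose, its probability is *q* in every group. Expected counts are 21 × 0.2 = 4.2 in each, so equal intolerance shows as equal.

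**The case against.** The strongest reply is that tolerability does not rest on withdrawals. The primary safety endpoint is the frequency and severity of AEs and SAEs. ISRs are adverse events of special interest, recorded and graded in the same way at every dose (Protocol 8.3.8), so a reaction that prompts a reduction is still reported. A caregiver questionnaire on acceptability and tolerability of the injection is collected about every three months (Protocol 8.1.7), and patient- and observer-reported assessments are summarised by dose (9.3.6). This stands. A reader might infer that the safety endpoint counts only withdrawals, or that daily dosing would look best tolerated overall. The documents support neither reading. What remains is that AE counts show that a reaction occurred, not whether the child could stay on the regimen.

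Other points also limit the claim:

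- Step-down is optional, and severe ISRs are expected to lead to withdrawal at any dose (Protocol 7.1). Both would shrink the gradient; neither reverses it by assigned dose.
- Entrants have completed C4181005 and are judged to keep a positive risk:benefit profile, so some intolerant children may already have been filtered out. The only paediatric data cited (Protocol 2.2.1) are six children on QW or BIW, with all AEs mild.
- SAP 5.6.1 leaves AE reporting to sponsor standards that the documents do not reproduce, and those may include a reduction table. The supportable statement is that neither document names one.
- Safety analysis is descriptive, and nothing says that the therapeutic dose will be chosen from withdrawal counts in this study.
- A summary by assigned dose needs a rule for children moved to a therapeutic dose. Without one, later events would be credited to the wrong regimen.

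**Conclusion.** The concern holds for the AE-withdrawal comparison and no further. Protocol 6.5 turns the same trigger into a possible reduction at two doses and a discontinuation at the third. Only the discontinuation is a named summary, and the grouping rule does not cover children who step down. The rates by dose are therefore not comparable. By assigned dose they tend to favour the higher doses if any intolerance resolves after a step-down. By dose received, withdrawals after a step-down may land on the lower dose.

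The direction by assigned dose needs only that step-downs are used and *r* is below 1. The size is unknown. A reader might take the fourfold gradient (4.2 against 1.05) as the expected distortion. It rests on assumed rates and group sizes, narrows to 4.2 against 2.7 at 80% persistence, and vanishes if no case resolves. It is also computed by assigned dose, which is not the grouping the plan specifies.

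The change should be made: it is cheap and concerns a primary objective.

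**What to change.** **In SAP 5.6:**

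- Add a by-dose summary of first AE-related dose reduction or permanent discontinuation, and the same for ISR-related events alone, with time to event. Group by the dose assigned from C4181005 (the RAS), and censor at any sponsor-directed move to a therapeutic dose.
- Keep AE withdrawals as a component, footnoted that the 6.5 step-downs exist only from the two higher doses.
- State how AEs and withdrawals after a step-down are attributed under grouping by dose received.

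**In Protocol 8.3.8:** add dose reduction to the recorded consequences of an ISR.

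**To reconcile, without any change to the ladder on account of this point:**

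- The QD row of 6.5 names no end step, while the other two rows do.
- 6.5 has the QW child discontinued from the study. Protocol 7.1 says both that a participant who permanently stops treatment stays in for the final follow-up visit and that such a participant does not stay for further evaluation.

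**Cost:** a small set of safety summaries, two SAP sentences and one CRF response option. Reduction dates are already collected and the RAS is already defined.
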